15.2.4. Pharmacokinetics Analysis

PK parameters for ACE-536, such as maximum serum concentration (C_{max}), time to maximum concentration (t_{max}), and area under the concentration/time curve (AUC), will be estimated using non-compartmental and/or single compartment analysis, as appropriate. Dose proportionality may be assessed using the exposure data (e.g., C_{max} , AUC) if sufficient dose levels are studied. Descriptive statistics will be provided for serum concentrations and PK parameters. The relationship between ACE-536 exposure and response (i.e., safety, efficacy, and biomarkers) may be explored, as appropriate.

15.2.5. Anti-drug Antibody Analysis

The results of anti-drug and neutralizing antibody testing for ACE-536 and human ActRIIB protein versus time will be presented. Exploratory analysis will be performed on the potential effect of ADA on ACE-536 PK and drug exposure if ADA tests are deemed positive.

15.3. Determination of Sample Size

There is no formal sample size calculation for the study although up to 72 patients may participate from the A536-04 study.

15.4. Interim Analysis

Safety and erythroid response data will be reviewed periodically throughout the study. A formal interim analysis of the safety and efficacy data will be performed to support registration filings.

15.5. Deviation from Original Analysis Plan

A formal Statistical Analysis Plan (SAP) for the analysis and presentation of data from this study will be prepared before the database lock. Deviations from the statistical analyses outlined in this protocol will be indicated in this plan; any further modifications will be noted in the final clinical study report.

16. SOURCE DOCUMENTATION AND INVESTIGATOR FILES

16.1. Study Monitoring

The clinical monitor will arrange to visit the clinical sites at regular intervals during the study. The monitoring visits must be conducted according to the applicable ICH and GCP guidelines to ensure protocol adherence, quality of data, drug accountability, compliance with regulatory requirements, and continued adequacy of the clinical sites and their facilities. During these visits, CRFs and other data related to the study will be reviewed and any discrepancies or omissions will be resolved. The clinical monitor will be given access to study-relevant source documents (including medical records) for purposes of source data verification.

16.2. Audits and Inspections

The investigators and clinical sites will permit trial-related monitoring, audits, IEC review, and regulatory inspections as requested by the United States Food and Drug Administration (FDA) or other health authorities and the sponsor or designee. In addition to CRFs, the clinical site will permit direct access to source data/documents (i.e., original medical records, laboratory reports, hospital documents, progress reports, signed ICFs, etc.). During and/or after completion of the study, quality assurance officers named by the sponsor or the regulatory authorities may wish to perform on-site audits. The investigator is expected to cooperate with any audit and provide assistance and documentation (including source data) as requested.

17. QUALITY CONTROL AND QUALITY ASSURANCE

17.1. Data Quality Control and Quality Assurance

17.1.1. Investigator Responsibility

The investigator is responsible for ensuring the study is conducted according to the protocol, Code of Federal Regulations, GCP, and applicable regulatory requirements. The investigator's responsibilities are outlined in these documents and must include the responsibility to obtain a signed informed consent prior to patient participation in the study.

17.1.2. Protocol Modifications

The investigator should not modify the protocol without agreement from the sponsor and prior review or approval by the IEC, unless an emergency situation requires protocol modification to ensure the safety of patients. Any deviations from the protocol should be documented by the investigator or designee.

18. CONFIDENTIALITY

To maintain patient privacy, all CRFs, study drug accountability records, study reports and communications will identify the patient by the assigned patient identification number. The investigator will grant clinical monitor(s) and auditor(s) from the sponsor or designee and regulatory authorities access to the patient's original medical records for verification of data gathered on the CRFs and to audit the data collection process. The patient's confidentiality will be maintained and will not be made publicly available. The patient's medical information will only be released to the extent permitted by the applicable laws and regulations.

All information regarding the investigational product supplied by the sponsor to the investigator is privileged and confidential information. The investigator agrees to use this information to accomplish the study and will not use it for other purposes without consent from the sponsor. It is understood that there is an obligation to provide the sponsor with complete data obtained during the study. The information obtained from the clinical study will be used towards the development of the investigational product and may be disclosed to regulatory authorities, other investigators, corporate partners, or consultants as required.

A description of this clinical trial will be available on <http://www.ClinicalTrials.gov>, as required by U.S. Law. This Web site will not include information that can identify patients, but may include a summary of the results.

Publication Policy

All information concerning ACE-536 is considered confidential and shall remain the sole property of the sponsor. The investigator(s) agree to use this information only in conducting the study and shall not use it for any other purposes without the sponsor's written approval. The investigator(s) agree not to disclose the sponsor's confidential information to anyone except to persons involved in the study that need such information to assist in conducting the study, and then only on like terms of confidentiality and non-use.

It is understood by the investigator(s) that the information developed from this clinical study will be used by the sponsor in connection with the development of ACE-536, and therefore may be disclosed as required to regulatory agencies. To allow for the use of the information derived from clinical studies, it is understood that there is an obligation to provide the sponsor with complete test results and all data developed in the study.

No publication or disclosure of study results will be permitted except as specified in a separate, written, agreement between the sponsor and the investigator(s).

19. PROTOCOL AMENDMENTS

Protocol amendments that impact patient safety, change the scope of the investigation, or affect the scientific quality of the study must be approved by the IEC and submitted to the appropriate regulatory authorities before implementation.

In the event that the protocol needs to be modified immediately to eliminate an apparent hazard to a patient, the sponsor will implement the protocol change and subsequently amend the protocol and notify the regulatory authorities and/or the IEC, as appropriate.

20. DATA HANDLING AND RECORDKEEPING

20.1. Case Report Form Completion

CRFs will be completed for each enrolled patient. It is the investigator's responsibility to ensure the accuracy, completeness, and timeliness of the data reported in the patient's CRF. Source documentation supporting the CRF data should indicate the patient's participation in the study and should document the dates and details of study procedures, AEs, and patient status.

Investigators will maintain copies of the CRFs at the clinical site. For patients who discontinue or terminate from the study, the CRFs will be completed as much as possible, and the reason for the discontinuation or termination clearly and concisely specified on the appropriate CRF.

20.2. Retention of Records

The investigator will maintain all study records according to ICH-GCP and applicable regulatory requirements. Records will be retained for at least 2 years after the last marketing application approval or 2 years after formal discontinuation of the clinical development of the investigational product, or according to applicable regulatory requirements. If the investigator withdraws from the responsibility of keeping the study records, custody must be transferred to a person willing to accept the responsibility. The sponsor must be notified in writing if a custodial change occurs.

21. STUDY FINANCE AND INSURANCE

21.1. Study Finance

The costs necessary to perform the study will be agreed with each Investigator and will be documented in a separate financial agreement that will be signed by the Investigator and Acceleron Pharma Inc. or designee, prior to the study commencing.

21.2. Insurance

The Sponsor has insurance coverage for study related ACE-536 induced injury and other liabilities incurred during clinical studies which will provide compensation for any study related injury according to the guidelines set out by the Association of the British Pharmaceutical Industry (ABPI), namely “Clinical Studies Compensation for Medicine Induced Injury”.

23. APPENDICES

23.1. Appendix 1: National Cancer Institute (NCI) Common Terminology Criteria for Adverse Events (CTCAE)

See <http://evs.nci.nih.gov/ftp1/CTCAE>

1. INTRODUCTION

This statistical analysis plan (SAP) describes the statistical methods to be used for the analysis of Acceleron Protocol A536-06. This SAP should be read in conjunction with the study protocol and electronic case report form (eCRF). This version of the plan has been developed using the protocol amendment 05 dated 12 September 2017 and eCRF v7 dated 14 March 2018. Any further changes to the protocol or eCRF may necessitate updates to the SAP.

The SAP will be signed off before the study database lock. Any deviations from the SAP will be described and justified in the final clinical study report (CSR).

2. STUDY OBJECTIVES

Primary Objective:

- To evaluate the long-term safety and tolerability of ACE-536 in patients with β -thalassemia who were previously enrolled in study A536-04.

Secondary Objectives:

- To evaluate erythroid response defined as the proportion of patients with:
 - Mean hemoglobin increase ≥ 1.5 g/dL over a continuous 12-week interval compared to baseline in non-transfusion dependent (NTD) patients, not influenced by red blood cell (RBC) transfusion, OR
 - Reduction in RBC transfusion burden by $\geq 50\%$ over a continuous 12-week interval compared to the 12 weeks prior to the start of treatment in transfusion dependent (TD) patients.
- To evaluate erythroid response defined as proportion of patients with:
 - Mean hemoglobin increase ≥ 1.5 g/dL over a continuous 8-week interval compared to baseline in NTD patients, not influenced by RBC transfusion, OR
 - Reduction in RBC transfusion burden by $\geq 20\%$ over a continuous 8-week interval compared to the 8 weeks prior to the start of treatment in TD patients.
- To evaluate the time to erythroid response and duration of erythroid response.
- To evaluate the mean change from baseline over an 8- or 12-week period in hemoglobin level in NTD patients not influenced by RBC transfusion
- To evaluate the mean % change from baseline in transfusion burden over an 8- or 12-week period in TD patients.
- To evaluate the mean change in pre-transfusion hemoglobin levels in TD patients
- To evaluate changes in markers of erythropoiesis, hemolysis, iron overload, and iron metabolism
- To examine the pharmacokinetic (PK) profile of ACE-536 in patients with β -thalassemia

Exploratory Objectives:

- To evaluate biomarkers related to the transforming growth factor beta (TGF- β) superfamily
- To evaluate patient self-reported quality of life using tools including but not limited to the Functional Assessment of Cancer Therapy-Anemia Scale (FACT-An) and Short Form (36) Health Survey (SF-36) questionnaires
- To evaluate change in extramedullary hematopoiesis (EMH) mass size by MRI
- To evaluate change in spleen size by MRI
- To evaluate change in bone mineral density (BMD) by DXA
- To evaluate change in leg ulcers
- To evaluate change in the 6-minute walk test (6MWT) distance in NTD patients

3. OVERALL STUDY DESIGN

This open-label extension study will evaluate the effects of up to 60 months of ACE-536 treatment in patients with β -thalassemia previously enrolled and treated with ACE-536 for up to 3 months in study A536-04. The base study (A536-04) is a phase 2, open-label, ascending dose study to evaluate the effects of ACE-536 in patients with β -thalassemia. A total of up to 64 patients may be enrolled in study A536-04 and may be eligible for study A536-06.

3.1. Study Design

Consenting patients that meet the A536-06 eligibility criteria may immediately roll over from A536-04 to study A536-06 following the last ACE-536 dose. These patients may forego the End of Study (EOS) visit in study A536-04 to begin study A536-06. For these patients, Cycle 1 Day 1 (C1D1) of study A536-06 may take place 28 (\pm 7) days after the last dose administered in study A536-04, which may coincide with the patient's A536-04 End of Treatment (EOT) visit. These patients are considered "patients without treatment interruption".

Patients who complete the EOS visit for study A536-04 and are \geq 28 days post EOS visit are considered "patients with treatment interruption" and will be re-assessed for eligibility by meeting all eligibility criteria plus additional inclusion criteria, as defined in Section 9.3 of the protocol.

Patients who do not meet the above criteria (e.g., $>$ 35 days after last dose in study A536-04 and $<$ 28 days post EOS visit in study A536-04) may still participate, but should be treated as patients with treatment interruption and should not begin study A536-06 C1D1 until they have reached \geq 28 days post EOS visit from study A536-04 so that new baseline assessments can be measured.

For patients without treatment interruption, transfusion status (NTD or TD) will carry-over from the base study A536-04. For NTD patients with treatment interruption, transfusion status will be reassessed prior to C1D1 of study A536-06. NTD patients with treatment interruption are defined as patients who require transfusion of $<$ 4 units of RBCs over the 8 weeks prior to Cycle

1 Day 1 of study A536-06. For TD patients with treatment interruption, transfusion status will carry-over from the base study A536-04.

A patient without treatment interruption may continue to be dosed with ACE-536 at the same dose level (rounded to nearest A536-06 starting dose level) administered at their last dose in study A536-04 (unless a dose reduction is required based upon patient dose modification rules from study A536-06). All patients with treatment interruption will be initially treated with ACE-536 at a starting dose level of 0.8 mg/kg which has been determined to be safe and well tolerated by the Safety Review Team (SRT) based on data from study A536-04. Examples of possible starting dose levels with dose modifications (reductions and titrations) are below for reference.

Table 1: Examples of Possible Starting Dose with Dose Modifications (Reductions and Titrations)

3 rd Dose Reduction	2 nd Dose Reduction	1 st Dose Reduction	Starting Dose Level	1 st Dose Titration	2 nd Dose Titration
0.2 mg/kg	0.4 mg/kg	0.6 mg/kg	0.8 mg/kg	1.0 mg/kg	1.25 mg/kg
0.4 mg/kg	0.6 mg/kg	0.8 mg/kg	1.0 mg/kg	1.25 mg/kg	
0.6 mg/kg	0.8 mg/kg	1.0 mg/kg	1.25 mg/kg		

- Starting dose level for TD and NTD patients to be determined based on data from study A536-04 (range: 0.2-1.25 mg/kg).
- Starting dose level for patients without treatment interruption will be last dose level (rounded to nearest A536-06 starting dose level) administered in study A536-04 unless a dose reduction is required based upon patient dose modification rules from study A536-06.
- Patients may be titrated up and down dose levels as required per protocol to meet dose modification and titration rules.
- Patients who require more than 2 dose reductions due to an AE should be discontinued from treatment and complete the EOT and EOS visits.
- The maximum dose titration will not exceed the maximum dose level tested in base study A536-04.
- Each TD patient will have a defined “pre-transfusion hemoglobin threshold” which will be calculated based on transfusion history and will be used for determining when to transfuse during the study. The baseline pre-transfusion hemoglobin threshold will be the mean of all documented pre-transfusion hemoglobin values during the 12 weeks prior to C1D1 of base study A536-04 (for patients without treatment interruption) or study A536-06 (for patients with treatment interruption). During treatment, if the pre-transfusion hemoglobin level is increased by ≥ 1 g/dL compared to the baseline pre-transfusion hemoglobin threshold for that patient, transfusion should be delayed by a minimum of 7 days and/or the number of units transfused should be reduced by 1 or more RBC units. Patients may be transfused at the investigator’s discretion for symptoms related to anemia or other requirements (e.g., infection).

Patients will participate in the extension study A536-06 for up to 97 months, including a 28-day (1 month) screening period, a 60-month treatment period and a 3-year (36 months) follow-up period.

3.2. Treatment Discontinuation

Patients were informed that they have the right to withdraw from the study at any time for any reason without prejudice to their medical care.

A patient may be discontinued from treatment for any of the following reasons:

- Patient's request
- Patient's unwillingness or inability to comply with the protocol
- Pregnancy
- Use of prohibited medication (e.g., hydroxyurea)
- Medical reason or adverse event, at the discretion of the investigator and/or the medical monitor
- Hypersensitivity reaction to study drug
- At the discretion of the sponsor (e.g., termination of the study or a dose level)

A patient may be withdrawn from the study for any of the following reasons:

- Patient's request
- Patient's unwillingness or inability to comply with the protocol
- Death
- Loss to follow-up
- At the discretion of the sponsor (e.g., termination of the study)

Patients who discontinue treatment early should complete the end of treatment (EOT) follow-up visit at the time of discontinuation and then complete the end of study (EOS) follow-up visit approximately 28 days later.

3.3. Sample Size

There is no formal sample size calculation for the study although up to 64 patients may participate from the A536-04 study.

4. ANALYSIS POPULATIONS

4.1. The Intent-To-Treat (ITT) Population

The intent-to-treat (ITT) population consists of all patients enrolled in the study who received at least one dose of ACE-536 in the A536-06 study. This population will be used for all efficacy analysis.

For patients who directly rolled over from A536-04 study, both A536-04 study and A536-06 study data will be included for the analysis.

For interrupted patients, only A536-06 study data will be included for the analysis.

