9.3.2. Inclusion Criteria

All patients must meet the following criteria:

1. Completion of the treatment period in the base study A536-04.
2. Females of child bearing potential (defined as sexually mature women who have not undergone hysterectomy or bilateral oophorectomy, or are not naturally postmenopausal ≥ 24 consecutive months) must have negative urine or blood pregnancy test prior to enrollment and use adequate birth control methods (abstinence, oral contraceptives, barrier method with spermicide, or surgical sterilization) during study participation and for 12 weeks following the last dose of ACE-536. Males must agree to use a latex condom during any sexual contact with females of child-bearing potential during study participation and for 12 weeks following the last dose of ACE-536, even if he has undergone a successful vasectomy. Patients must be counseled concerning measures to be used to prevent pregnancy and potential toxicities prior to the first dose of ACE-536.
3. Patient is able to adhere to the study visit schedule, understand and comply with all protocol requirements.
4. Patient understands and is able to provide written informed consent.

All patients with treatment interruption must also meet the following criteria:

Patients with treatment interruption (defined as patients who complete the EOS visit for study A536-04 and are ≥ 28 days post EOS visit) must also meet the following criteria:

5. Mean hemoglobin concentration < 10.0 g/dL of 2 measurements (not influenced by RBC transfusion) (one performed within one day prior to Cycle 1 Day 1 and the other performed during the screening period [Day -28 to Day -1]) in NTD patients.
6. Adequate folate levels or on folate therapy.
7. Platelet count $\geq 100 \times 10^9/L$ and $\leq 1,000 \times 10^9/L$.
8. Aspartate aminotransferase (AST) or alanine aminotransferase (ALT) $< 3 \times$ upper limit of normal (ULN).
9. Serum creatinine $\leq 1.5 \times$ ULN.
10. Ejection fraction $\geq 50\%$ by Echocardiogram (ECHO) or Multi gated acquisition scan (MUGA).

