9.3.3. Exclusion Criteria

All patients must not meet any of the following criteria:

1. Discontinuation/withdrawal from study A536-04 due to patient request, patient unwillingness or inability to comply with the protocol, pregnancy, use of prohibited medication (e.g., hydroxyurea), medical reason or AE, hypersensitivity reaction to the study drug, at the discretion of the sponsor, or loss to follow-up prior to completion of the treatment period.
2. Any clinically significant pulmonary (including pulmonary hypertension), cardiovascular, endocrine, neurologic, hepatic, gastrointestinal, infectious, immunological (including clinically significant allo- or auto-immunization) or

genitourinary disease considered by the investigator as not adequately controlled prior to Cycle 1 Day 1.

3. Symptomatic splenomegaly.
4. Splenectomy within 56 days prior to Cycle 1 Day 1.
5. Major surgery (except splenectomy) within 28 days prior to Cycle 1 Day 1. Patients must have completely recovered from any previous surgery prior to Cycle 1 Day 1.
6. Patients receiving or planning to receive hydroxyurea treatment. Patients must not have had hydroxyurea within 90 days of Cycle 1 Day 1.
7. For patients with treatment interruption: Iron chelation therapy if initiated within 56 days prior to Cycle 1 Day 1.
8. Cytotoxic agents, systemic corticosteroids, immunosuppressants, or anticoagulant therapy such as warfarin or heparin within 28 days prior to Cycle 1 Day 1 (prophylactic aspirin up to 100 mg/day and low molecular weight (LMW) heparin for superficial venous thrombosis (SVT) is permitted).
9. Treatment with another investigational drug (including sotatercept [ACE-011]) or device, or approved therapy for investigational use \leq 28 days prior to Cycle 1 Day 1, or if the half-life of the previous investigational product is known, within 5 times the half-life prior to Cycle 1 Day 1, whichever is longer at any time between the end of treatment of the base study A536-04 and Cycle 1 Day 1.
10. Known positive for human immunodeficiency virus (HIV), active infectious hepatitis B (HBV) or active infectious hepatitis C (HCV).
11. Uncontrolled hypertension defined as systolic blood pressure (SBP) \geq 150 mm Hg or diastolic blood pressure (DBP) \geq 100 mm Hg.
12. Known history of thromboembolic events \geq grade 3 according to the National Cancer Institute-Common Terminology Criteria for Adverse Events (NCI-CTCAE) v.4.0 (current active minor version).
13. Pregnant or lactating females.

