15.2.3. Secondary Analysis

All efficacy analyses will be performed for the EE and mITT populations.

Efficacy will be evaluated by determining the proportion of β -thalassemia patients who have an erythroid response, defined as 1) a mean hemoglobin increase ≥ 1.0 g/dL or ≥ 1.5 g/dL over an 8-week or 12-week period as compared to baseline, not influenced by RBC transfusion in NTD patients or 2) $\geq 20\%$ or $\geq 50\%$ reduction in RBC transfusion burden over an 8-week or 12-week period as compared to the 8-week or 12-week period pretreatment in TD patients.

Baseline hemoglobin for NTD patients will be the average of two or more measurements performed during the screening period for base study A536-04 (for patients without treatment

interruption) or study A536-06 (for patients with treatment interruption). Hemoglobin measurements within 2 weeks following RBC transfusion will be excluded.

Transfusion burden for TD patients will be defined as the ratio of RBC transfusion units (or mLs) transfused during an interval divided by the duration of that interval, where the interval may be during the pretreatment period or the treatment plus follow-up period. The interval during the pretreatment period will be defined as the 8 or 12 weeks prior to Cycle 1 Day 1 of base study A536-04 (will also be analyzed using pretreatment period of study A536-06 for patients with treatment interruption). An interval during the treatment plus follow-up period will be defined as an 8-week or 12-week interval after Cycle 1 Day 1 of study A536-06.

The erythroid response, as defined above, will also be evaluated using other pre-treatment and on-treatment intervals and other % reductions in RBC units transfused, including 100% (transfusion-free).

The erythroid response will be summarized using both a point estimate and its exact 95% CI based on binomial distribution.

No direct comparison testing with concurrent or historical controls will be performed.

Analysis of other secondary efficacy/PD endpoints will include:

- Time to erythroid response and duration of erythroid response
- Change/percent change from pretreatment in mean transfusion burden in TD patients
- Change in mean hemoglobin level in NTD patients
- Change in pre-transfusion hemoglobin levels in TD patients (including analysis of patient subset with < 20% change in transfusion burden)
- Change from baseline in erythropoiesis parameters, including EPO, reticulocytes, nucleated RBCs, and soluble transferrin receptor

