4.2. Safety Population

Same as ITT population.

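### SAP 4.1 lets direct rollovers count as TD responders on A536-04 time, although Protocol 15.2.3 counts only intervals after A536-06 Cycle 1 Day 1, and the SAP does not declare the change

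*SAP*

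**What the plan says.** **Who is analysed.** SAP 4.1 defines the ITT population as "all patients enrolled in the study who received at least one dose of ACE-536 in the A536-06 study" and uses it for efficacy. SAP 4.2 defines the safety population in four words: "Same as ITT population".

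**Which data are analysed.** SAP 4.1 sets two rules by entry route. For direct rollovers: "For patients who directly rolled over from A536-04 study, both A536-04 study and A536-06 study data will be included for the analysis". For the others: "For interrupted patients, only A536-06 study data will be included for the analysis". SAP 5.1 gives rollovers their A536-04 baseline. SAP 5.7.2.1 then accepts any rolling 8-, 12- or 24-week interval for response and sets no earliest start.

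**What the protocol says.** Protocol 15.2.3 takes the TD pretreatment interval before Cycle 1 Day 1 (C1D1) of A536-04. It says that an interval in the treatment plus follow-up period "will be defined as an 8-week or 12-week interval after Cycle 1 Day 1 of study A536-06". Protocol 15.5 requires the SAP to indicate deviations from the protocol's analyses. SAP 5.12.6 names two changes: the baseline hemoglobin definition, and removal of the efficacy-evaluable population with mITT renamed ITT.

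**Who can enter.** Inclusion criterion 1 in Protocol 9.3.2 is "Completion of the treatment period in the base study A536-04". Exclusion criterion 1 in Protocol 9.3.3 bars patients who left A536-04 early for listed reasons, among them "medical reason or AE, hypersensitivity reaction to the study drug, at the discretion of the sponsor, or loss to follow-up".

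**The concern.** The protocol anchors the two ends of the TD comparison in different studies: pretreatment before A536-04, on-treatment in A536-06. The SAP keeps the first anchor and moves the second for one entry route only. Three things follow.

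- A rollover can be counted as an A536-06 responder on an interval that ended before A536-06 began.
- One response rate mixes patients scored over two studies with patients scored over one.
- The added time belongs only to patients who completed A536-04 and then entered A536-06. Other base-study patients are in no denominator.

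A reader of the extension report would take the TD response rate as evidence about response during long-term treatment. Protocol 15.4 foresees use of the efficacy data in registration filings, so what the rate can support matters even though it is descriptive.

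**Working it through.** The plan gives no sample size, power or expected response figure to reproduce. The check therefore counts days and windows from the schedules and then illustrates the size.

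**1. Inputs from the documents**
- A536-04 dosing every 21 days for five cycles (SAP Appendix 3): Cycle 5 Day 1 = 1 + 4×21 = Day 85, and EOT = 85 + 28 = Day 113. Both match the schedule.
- A536-06 C1D1 for rollovers is 28 (±7) days after the last A536-04 dose (Protocol 9.1): Day 113, range Day 106 to 120.
- Last A536-06 cycle: 1 + 86×21 = Day 1807, which matches the protocol schedule. SAP 5.7 ends efficacy scoring no later than 56 days after the last dose: 1807 + 56 = Day 1863.

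**2. Windows wholly before A536-06 C1D1**

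With P days before C1D1 and window length L, the number of windows is P − L + 1.

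| Gap after last A536-04 dose | P | 8-week (L = 56) | 12-week (L = 84) |
|---|---|---|---|
| 21 days | 105 | 50 | 22 |
| 28 days | 112 | 57 | 29 |
| 35 days | 119 | 64 | 36 |

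At P = 112, a further 112 − 29 = 83 twelve-week windows start before C1D1 and run across it.

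**3. Share of scored time**
- Rollover who reaches Cycle 87: 112/(112 + 1863) = 5.7% (5.3% to 6.0% over the range of gaps).
- Rollover with 12 weeks in A536-06: 16/(16 + 12) = 57%.
- Weeks 13-24, if counted from the first A536-04 dose, are Days 85-168. Days 85-112 precede C1D1: 28/84 = 33% (25% to 42%). For interrupted patients it is 0%.

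**4. Direction**

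Response needs one qualifying interval. Adding intervals while the patients stay the same can turn a non-responder into a responder, never the reverse. The pooled any-interval rate is at least as high as the A536-06-only rate.

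**5. Size, by simulation under assumptions**

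Assumed, not from the documents: no drug effect; transfusions on average every 21 days, SD 3 or 6 days; 1, 2 or 3 units with probability 0.15, 0.70 and 0.15; 16 weeks of A536-04 time; 4,000 simulated patients per setting. The mean is 2 units per 21 days, or 56/21×2 = 5.3 units per 8 weeks, above the TD threshold of 4 in SAP 5.1.

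Chance of at least one 12-week window with a reduction of 50% or more (SD 3 / SD 6):

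| Weeks in A536-06 | A536-06 only | Pooled | Difference, points |
|---|---|---|---|
| 12 | 0.8% / 2.2% | 9.8% / 16.1% | 9.0 / 13.9 |
| 24 | 8.8% / 11.5% | 15.4% / 22.6% | 6.6 / 11.1 |
| 48 | 17.4% / 23.9% | 22.3% / 30.3% | 4.9 / 6.4 |
| 96 | 30.6% / 43.7% | 33.7% / 47.2% | 3.1 / 3.5 |

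The 20% criterion over 8 weeks behaves the same way: 65.9% / 59.2% becomes 85.3% / 84.4% with 12 weeks in A536-06, and 95.0% / 96.3% becomes 95.5% / 96.9% with 96 weeks.

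These are per-rollover figures. The documents do not give the rollover share p among TD patients. The change in the overall rate is p times the difference, so it lies between zero and the value shown.

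**The case against.** **Arguments for leaving the plan as it is**
- Under the SAP each route is scored from the first dose after its own baseline, which is coherent. Starting rollovers at A536-06 C1D1 begins about 16 weeks into their treatment. Weeks 13-24 would then be about weeks 29-40 after first dose (16 + 13 to 16 + 24), and time to response would be left-truncated for anyone already responding. This stands, and it is why the fix below does not impose A536-06 time on those endpoints.
- Protocol 15.2.3 also allows response to be evaluated over other pretreatment and on-treatment intervals. It does, but in addition to the defined interval, not in its place.
- The pooling rule is openly stated in SAP 4.1, there is no primary efficacy endpoint and no test is planned. True, so no type I error claim is affected. It is still not identified as a departure from the protocol.

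**Stronger readings that the documents do not support**
- A reader might infer that the rate is conditioned on response because responders are likelier to roll over. Eligibility turns on completing A536-04 treatment and not having withdrawn, starting with "Discontinuation/withdrawal from study A536-04 due to patient request". It does not depend on response. The same criteria apply to interrupted patients and whichever days are scored, so changing the scored time would not remove that selection.
- A reader might infer that the planned tables show zero adverse-event withdrawals in the early months by construction. That requires A536-04 events to be pooled. SAP 4.2 can be read as defining a set of patients only, and SAP 5.8.1 counts events after the C1D1 dose without naming the study. Pooling is implied at most, and the plan needs to say which is meant.
- A reader might take Protocol 15.2.3 to rule out A536-04 time for NTD hemoglobin and for safety. The sentence concerns TD transfusion burden. The protocol states no on-treatment start for NTD response, and Protocol 15.2.2, which governs safety, sets no such window.

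**Conclusion.** The point holds for TD erythroid response. The SAP scores direct rollovers over time that the protocol's definition leaves out, scores interrupted patients differently, and does not declare the departure. The counts of 29 and 57 windows rest on five A536-04 cycles and C1D1 on Day 113; other permitted gaps give 22 to 36 and 50 to 64. The effect on an any-interval rate is upward or nil. Under the simulation's assumptions it is about 9 to 14 points per rollover for a 50% reduction over 12 weeks when A536-06 lasts 12 weeks, and about 3 points when it lasts 96 weeks. It is small for patients who stay long and matters most for those who leave early.

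For NTD response there is no literal conflict, only the same mixture of scored time. For adverse events the time origin is unclear, which is a gap in wording and not a demonstrated bias. Keeping the A536-04 baseline for rollovers is sound and agrees with the protocol.

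**What to change.** - **SAP 5.7.2.1, TD:** keep the A536-04 baseline for rollovers. Report any-interval response using only intervals that start on or after A536-06 C1D1, for both entry routes, as the Protocol 15.2.3 result.
- **SAP 5.7.2.1, NTD:** give the same A536-06-only version as a sensitivity analysis.
- **Pooled result:** present A536-04 plus A536-06 separately, labelled as conditional on completing A536-04 and entering A536-06. State its time origin for weeks 13-24, weeks 37-48 and, in SAP 5.7.2.2, time to response, where the first dose date does not name a study.
- **SAP 5.8:** tabulate adverse events and withdrawals from A536-06 C1D1. If A536-04 events are also shown, show them separately with the same label, because Protocol 14.5 has rollovers' events ongoing at A536-04 EOT entered again in A536-06.
- **SAP 5.12.6:** list the change and give the reason.

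The cost is SAP wording and one extra set of tables from data already held. The headline TD response rate may be slightly lower.
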